> chemotherapy without utilizing antiemetic medications (Eghbali et al., 2017; Herz, 2005; Hodge, McCarthy, & Pierce, 2014). Similar to aromatherapy, resilience, a person's ability to cope positively and adapt to their cancer diagnosis and treatment has shown to reduce symptoms such as anxiety and depression and increase the patient's well-being (Matzka et al., 2016). This study aims to investigate the effect of aromatherapy inhalation as a complimentary nonpharmaceutical intervention on CINV, resilience, and the use of antiemetics among patients with cancer receiving moderate to high emetogenic chemotherapy regimens outpatient. The study team used the National Comprehensive Cancer Network (NCCN) guidelines (NCCN,2020) to identify moderate and high emetogenic chemotherapy regimens.

5) Inclusion and Exclusion Criteria*

Inclusion includes:

- 18 years of age or older
- able to read and speak English or Spanish
- able to and willing to give informed consent
- currently undergoing moderate and high emetogenic chemotherapy (adjuvant or neoadjuvant)
- receiving three or more remaining cycles of chemotherapy
- symptoms of nausea or vomiting after the first chemotherapy infusion

Exclusion includes:

- unable or unwilling to give informed consent
- sensitivity to essential oils*
- olfactory disorders
- receiving chemotherapy for the first time
- undergoing low emetogenic chemotherapy regimens
- patients with hormone-sensitive cancers
- timely request of treating provider
- presently participating in an ongoing research study

(*) sensitivity to essential oils will be assessed when the study team members screen and recruit a potential participant.

6) Number of Subjects*

The total single-site sample size is 100.

7) Study-Wide Recruitment Methods*

Not applicable, for study's single site recruitment methods see section #24.

8) Study Timelines*

This research study can feasibly be completed in a proposed two-year time frame.

The duration period per participant will vary depending on their prescribed chemotherapy regimen, ranging from four to 12 weeks. If a participant is admitted to an SCCC's inpatient unit or has their chemotherapy temporally held during their study period, the study procedures will be postponed until their next scheduled outpatient CTU visit, see Table 1. The study will recruit 100 patients from a wide variety of racial and ethnic groups, gender, and over the age of 18.

Table 1. Participant Study Duration

Study Endpoints*

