The participants will complete a pre-assessment and demographic checklist that assesses their demographic information (e.g., race, ethnicity, age, and education level), essential oils sensitivity, and risk factors of CINV. The pre-assessment demographic checklist will provide the descriptive characteristics of the study's sample population.

• Additional data, such as medical history (e.g., diagnoses, allergies, medications, cancer history, and treatment regimen), family history, and recent outpatient and inpatient clinic or hospital visits, will be extracted from the electronic health record.

Aromatherapy Inhaler (Arm 2 – Intervention Only):

The study's aromatherapy inhaler can be used when participants' have their first sign of CINV and as needed. The aromatherapy inhaler contains a proprietary blend of peppermint, spearmint, lavender, and ginger essential oils that can last up to 6 months. Participants will twist open the cap, hold the inhaler below their nose, and take deep breaths to activate the aromatherapy inhaler. Once the participant is done, they will close the aromatherapy inhaler to turn it off. The aromatherapy vapors can be safely inhaled for as long as it takes to provide comfort and relief for the patient. There are no "limits" or duration restrictions for any essential oils in the blend. The aromatherapy inhalation amount can vary from brief intermittent use to continuous inhalation over several minutes. The aromatherapy inhaler has unlimited uses with no time limits. One inhalation of aromatherapy is equivalent to one dose. There are no known contraindications. At each study visit, the study team member will offer the participant a replacement aromatherapy inhalation device.

Antiemetic/Aromatherapy Diary (Arm 2 - Intervention Only):

The antiemetic/aromatherapy diary will allow the participants to record their weekly usage (date and time) of aromatherapy and antiemetic uses and evaluate the aromatherapy and type (name) of antiemetic medications. The evaluation will assess the effects of the aromatherapy on CINV by capturing the number of inhalations per nausea episode and asking the participants, 'Did the aromatherapy take away your nausea?' answers include: 'it took away my nausea completely' to 'it had no effect on my nausea.' If the participants cannot get relief from the aromatherapy, the participants will take the prescribed antiemetic, and the participants will document the type of antiemetic medication they needed.

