All endpoints will be evaluated using parametric analysis to examine the difference between the two conditions across the 3-time points for primary endpoints (CINV and Use of Antiemetics) and 2-time points for secondary endpoints (resilience, psychological distress, and quality of life). The analysis will be conducted using SPSS Version 26. For binary outcomes (CINV), logistic regression will be used. For continuous outcomes (antiemetic use, resilience, psychological distress, and quality of life) a Mixed ANOVA will be used with condition as the between-subjects variable and change over time on the outcome as the within-subjects variable. Sphericity and homogeneity of variance assumptions will be tested prior to interpretation of the results, and the

Greenhouse-Geisser correction will be implemented if Sphericity is violated. A type I error rate of .05 will be used to determine significance for all analyses.

Outcome	Measure	Type of measurement
CINV	MAT	Binary
Use of antiemetics	Antiemetic Diary	Continuous
Resilience	CD-RISC	Continuous
Psychological Distress	Visual Analog Scale	Continuous
Quality of Life	FACIT-G	Continuous

2. Analysis of the Primary Endpoint(s)

For CINV, logistic regression will be used to determine whether the use of aromatherapy decreases the risk for any of the following outcomes: acute nausea, delayed nausea, acute vomiting, or delated vomiting. For use of antiemetic medication, a Mixed ANOVA will be used to evaluate differences between conditions (aromatherapy group vs. treatment as usual) across the 3-time points (Visit 1, Visit 2, and Visit 3). Time x treatment effects will be evaluated as well as main effects.

3. Analysis of the Secondary Endpoint(s)

For resilience, psychological distress, and quality of life, a Mixed ANOVA will be used to evaluate differences between conditions (aromatherapy group vs. treatment as usual) across the 2-time points (Initial visit and final visit). Time x treatment effects will be evaluated as well as main effects

4. Baseline Descriptive Statistics

Participant demographic characteristics will be analyzed using descriptive statistics. Specifically, frequencies and percentages will be reported for categorical variables, and means and standard deviations will be reported for continuous variables.

12) **Provisions to Monitor the Data to Ensure the Safety of Subjects***

This section is not applicable. The risks of this study are minimal.

13) Withdrawal of Subjects*

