- ii. Potential participants will be identified using the weekly SCCC's CTU schedule notes, displaying patients' chemotherapy regimen summary (e.g., chemotherapy drug type, dosage, and frequency). The study team member will identify patients undergoing moderate to high emetogenic chemotherapy (adjuvant or neoadjuvant). Identified patients will be screened for eligibility criteria by reviewing the patients' medical records. If a patient meets all eligibility criteria, a study team member will approach the patient during their regular outpatient CTU visit and screen for essential oils sensitivity. In case the potential participant is interested and willing to consent immediately, the study team member will review the study's informed consent. Once the informed consent is

> signed, the participant will receive a copy of the informed consent form. If the potential participant needs additional time to think about the study, the study team member will follow up with the patient at their next scheduled chemotherapy infusion visit. At this time, if the potential participant is interested and still meets the eligibility criteria, the study team member will explain the study and review the informed consent process.

24) Local Number of Subjects

The total single-site sample size is 100 participants.

25) Confidentiality

All participants will be assigned a unique study ID number. Identifying information will be stored separately from other study data in a passwordprotected, encrypted Excel file. All data will be stored on secure servers at the University of Miami, Box. Additionally, the REDCap software will be utilized during the study to maximize data security. Only authorized study personnel will have access to identifying information throughout the study.

Choose the statements below that are applicable to this research:

26(a). Will the research collect protected health information or personally identifiable information from the EMR or from subjects at UHealth and/or JHS?

 \boxtimes Yes (If checked go to 26(b))

□ No (If checked, go to Section 27)

26(b). Check the box next to the correct statement below

Research Subjects will sign a HIPAA Authorization before the research will collect this data.

Research Subjects will not sign a HIPAA Authorization for this data collection and the research is requesting a waiver of HIPAA authorization from the IRB

26(c). How will the research store the data?

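### The primary CINV logistic regression and the antiemetic Mixed ANOVA name no baseline covariates, so they forgo modest efficiency and protection against chance imbalance that data already collected could provide

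*Combined protocol and SAP*

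**What the plan says.** **Collected.** Procedures Involved (section 9) says that the pre-assessment checklist covers age and other demographics, "essential oils sensitivity, and risk factors of CINV". The health-record extract includes "diagnoses, allergies, medications, cancer history, and treatment regimen". Data Management (section 11) names age and gender as demographic variables.

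**Use of these data.** Section 9 states: "The pre-assessment demographic checklist will provide the descriptive characteristics of the study's sample population". The baseline subsection of section 11 is also descriptive only.

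**Models.** Under Analysis of the Primary Endpoint(s) in section 11: "For CINV, logistic regression will be used to determine whether the use of aromatherapy decreases the risk for any of the following outcomes"; the outcomes are acute and delayed nausea and vomiting. No covariate is named, and the text does not say how the three visits enter this model. Antiemetic use, under the same heading, is analysed by Mixed ANOVA with condition and time.

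**Design.** Inclusion and Exclusion Criteria (section 5) admits moderate and high emetogenic regimens. Number of Subjects (section 6): "The total single-site sample size is 100". The section on protecting subjects' privacy describes an online randomiser and states no stratification. Table 2 shows the MAT tool and the diaries first collected at Visit 1, so neither outcome has a baseline score to adjust for.

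**The concern.** The protocol grades regimens by emetogenic potential and collects what it calls risk factors for CINV, so it treats both as bearing on the outcome. Neither the randomisation nor the analysis then uses them. If they are prognostic, two things are lost.

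- **Power.** A logistic model that omits a strong predictor has less power to detect a treatment effect than one that includes it. This matters more in a small trial with no stated power calculation.
- **Protection in the trial actually run.** Without stratification the arms can differ by chance in the share on highly emetogenic regimens. An unadjusted odds ratio carries that difference into the primary result.

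Silence on covariates also leaves their choice open until after the data have been seen.

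**Working it through.** **Inputs from the documents.** N = 100; "A type I error rate of .05 will be used to determine significance for all analyses"; background CINV rate 40% and nausea rate 71% (section 4), used as two control-risk scenarios. The plan gives no power, effect size, allocation ratio or dropout, so there is no stated power figure to reproduce.

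**Assumptions.** 1:1 allocation (50 per arm), two-sided test, one binary outcome per patient, a 50:50 regimen mix, and prognostic strengths as shown.

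**Step 1. Unadjusted power for a 20-point fall.** Power = Φ{[d − 1.96√(2p̄(1−p̄)/n)] / √[(p₁(1−p₁)+p₂(1−p₂))/n]}, n = 50.
- 40% vs 20%: (0.200 − 1.96×0.0917)/0.0894 = 0.23, power 0.59.
- 71% vs 51%: (0.200 − 1.96×0.0976)/0.0955 = 0.09, power 0.54.

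Power of 80% needs a fall from 40% to about 15%, or from 71% to about 44%.

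**Step 2. Power with and without adjustment, marginal risks held fixed.** About 4,000 simulated trials per cell, Wald test. Adjusted models include binary regimen class and one standardised risk score. Strengths: none; weak (regimen OR 2, log-OR 0.5 per SD); middle (3, 0.8); strong (4, 1.0). Entries are unadjusted → adjusted.

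| Risks | None | Weak | Middle | Strong |
|---|---|---|---|---|
| 40% vs 20% | 0.580 → 0.585 | 0.570 → 0.608 | 0.578 → 0.656 | 0.578 → 0.680 |
| 40% vs 15% | 0.801 → 0.804 | 0.809 → 0.839 | 0.802 → 0.865 | 0.802 → 0.881 |
| 71% vs 51% | 0.559 → 0.550 | 0.548 → 0.582 | 0.538 → 0.598 | 0.545 → 0.638 |
| 71% vs 44% | 0.787 → 0.774 | 0.800 → 0.815 | 0.798 → 0.845 | 0.808 → 0.872 |

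The gain runs from 1.5 points (0.815 − 0.800) to 10.2 points (0.680 − 0.578) when the covariates are prognostic. It is nil, within simulation error, when they are not.

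**Step 3. A second set-up.** Conditional OR fixed at 0.30, control risk about 65%, one risk score. Power goes from 81% to 81% (log-OR 0.5 per SD), 71% to 76% (1.0) and 59% to 70% (1.5): gains of 0, 5 and 11 points. Only the gap within each pair measures the cost of omission. Unadjusted power falls from 81% to 59% mainly because, with the conditional OR fixed, the marginal treated risk rises from about 37% to 44%; adjusted power falls too.

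**Step 4. Chance imbalance.** For a factor present in half of the patients, the SD of the difference in share is √(0.25×(1/50+1/50)) = 0.10. The exact hypergeometric probability of a gap of at least 10, 15 or 20 points is 0.32, 0.16 or 0.07.

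**Step 5. Effect of a 20-point imbalance with no true effect.** 30 of 50 against 20 of 50 on the higher-risk regimen, 6,000 simulated trials per row.

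| Event risk | Regimen OR | Average unadjusted OR | Type I error, unadjusted | Type I error, adjusted |
|---|---|---|---|---|
| 40% | 2 | 1.15 | 0.057 | 0.047 |
| 40% | 3 | 1.24 | 0.077 | 0.048 |
| 40% | 4 | 1.31 | 0.090 | 0.046 |
| 71% | 2 | 1.14 | 0.054 | 0.047 |
| 71% | 3 | 1.24 | 0.064 | 0.050 |
| 71% | 4 | 1.30 | 0.067 | 0.052 |

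Hand check: exp(0.20×ln 2) = 1.15 and exp(0.20×ln 4) = 1.32.

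**Step 6. Averaged over all randomisations, no true effect.** Type I error is 0.042 to 0.056 unadjusted and 0.047 to 0.054 adjusted.

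**Step 7. How many terms the data can carry.** Events among 100 patients range from 50×0.40 + 50×0.15 = 27.5 to 50×0.71 + 50×0.51 = 61. Vomiting may be rarer. With an assumed 15% control risk, OR 0.30 and six extra binary covariates, about 12% of simulated fits failed through separation; at 20%, about 3%; at 65%, none.

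**The case against.** The strongest reply is that randomisation makes the unadjusted comparison valid. That stands, and step 6 confirms it. A reader might infer from step 5 that the planned primary test is biased or has an inflated error rate. It does not: the excess applies only to allocations that happen to be imbalanced and disappears on averaging.

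The second reply is that every prognostic strength here is assumed. That also stands. Eligibility requires nausea or vomiting after the first infusion, which selects patients who already had CINV and may weaken the usual predictors. The background rates may not apply for the same reason. The documents do not show that age and gender are prognostic either; they are proposed because they are simple, already held and few.

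The third reply is that the plan is silent and does not forbid adjustment. This is correct. A reader might infer that covariates have been ruled out, or that the logistic model contains condition and time only; the text says neither. But silence does not prespecify anything, and the only use stated for the checklist is descriptive.

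Finally, the simulations adjust for a regimen class and a perfectly measured score, or for the score alone, not for the three covariates proposed. No simulation was run for the antiemetic model. The figures therefore indicate a plausible range and are not a forecast for this trial.

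**Conclusion.** The point holds as an inexpensive improvement in efficiency. Neither model names a baseline covariate, although regimen, CINV risk factors, age and gender are collected, emetogenic level varies by design and no stratification is stated. Adjustment would add 0 to about 11 points of power at 50 per arm, where unadjusted power for a 20-point fall is only 0.54 to 0.59. It would also hold type I error near 0.05 in the roughly 7% of allocations with a regimen gap of 20 points or more.

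The absence of named covariates is certain from the text; the size of the benefit is not. It rests on assumed odds ratios, a 50:50 regimen mix, equal arms and one outcome per patient. Repeated visits would change absolute power.

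**What to change.** Before any outcome data are seen, amend section 11 as follows.

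1. Include emetogenic level (moderate or high, derived from the extracted regimen as it stood at randomisation), age and gender as fixed covariates in the CINV logistic regression and the antiemetic Mixed ANOVA. Add no further risk factors unless event counts support them, and name any that are added.
2. Report the adjusted analysis as primary and the unadjusted one as supportive.
3. State the estimand: a conditional odds ratio or a standardised risk difference. The two odds ratios are not interchangeable. For 40% vs 20% the marginal OR is (0.20/0.80)/(0.40/0.60) = 0.375, while the conditional OR in the strong scenario of step 2 is 0.29.
4. Name a fallback for sparse vomiting outcomes, such as Firth penalised logistic regression or adjustment for emetogenic level only.
5. Give a rule for missing covariates.

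The cost is SAP wording, the small task of coding emetogenic class (the protocol already uses published guidelines to identify eligible regimens) and the move from a marginal to a conditional odds ratio if that estimand is chosen. No new visit, patient or procedure is needed.

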The study's initial visit will occur while patients are in the CTU or fast-track area as they get ready for treatment. The entire study will be explained to the patient when they are preparing for their chemotherapy regimen in a comfortable area provided by the SCCC. After answering the potential participants' questions, the study team member will go through the study's informed consent process if the participant is interested and willing to consent. The potential participants will have time to review and discuss informed consent. After the patient signs the informed consent, the participant will be randomized to the control or the intervention arm.

On the same day, the study team member will meet the participant in the CTU while they receive their infusion and provide both the control and intervention groups, access to complete, via iPad or laptop, the electronic pre-assessment and demographic form, psychological distress VAS, resilience scale, FACIT-G, and a study packet that includes the Antiemesis (MAT) tool, antiemetic diary or antiemetic/aromatherapy diary. The study packet will be completed and returned to the study team member on the participants' next scheduled chemotherapy infusion. The study team member will explain to the participants how to use the MAT tool and how to fill the antiemetic diary or antiemetic/aromatherapy diary. The study team member will go through the instructions to ensure that they understand the forms and how to complete them.

Arm 1 - Control group:

Participants in the control group will receive standard medical care, consisting of antiemetic medicine at the first sign of CINV on a schedule as prescribed by the healthcare provider. The study team member will review with the participant how to use the weekly study packet (e.g., MAT tool and antiemetic diary) and explain that a study team member will collect the packet on their next scheduled chemotherapy infusion.

Arm 2 - Intervention group:

Participants in the intervention group will receive an aromatherapy inhaler for complementary use with their antiemetic medication. Participants will be encouraged to use the aromatherapy inhaler at the first sign of CINV before taking their antiemetic medications that are labeled "as needed". The interventional group will be instructed that one normal inhale is equivalent to one dose of aromatherapy and must report essential oils sensitivity to a study team

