Additionally, there is a space to name other complementary methods used to relieve CINV and describe how the CINV was controlled in the antiemetic/aromatherapy diary.

MAT Tool:

The Antiemesis (MAT) tool created by the Multinational Association of Supportive Care in Cancer (Dranisaris et al., 2017) is a user-friendly and reliable tool designed to measure acute and delayed CINV across patients entire chemotherapy regimen. The MAT tool is available in English and Spanish languages. The MAT tool consists of eight items that assess participants' CINV (i.e., occurrence, duration, and frequency). Four items assess the participants' acute phase (i.e., first 24 hours after receiving chemotherapy), and the last four items assess the delayed phase (i.e., day 2 to day 4 after chemotherapy treatment). The MAT tool has been used as a communication tool to facilitate discussions about their CINV to their healthcare providers (Alafafsheh & Ahmad, 2016; Molassiotis et al., 2007; Yamaguchi et al., 2009). This MAT tool has shown good reliability and validity, with Cronbach alpha of 0.77-0.97 in 1200 patients with cancer (Alafafsheh & Ahmad, 2016; Dranisaris et al., 2017; Molassiotis et al., 2007; Yamaguchi et al., 2009).

Antiemetic Diary (Arm 1 - Control Only):

The antiemetic diary allows the participants to record their usage (date and time) and type (name) of antiemetic medications. Additionally, there is a space to name other

complementary methods used to relieve CINV and describe how the CINV was controlled in the antiemetic diary.

Resilience Scale:

The Connor-Davidson Resilience Scale (CD-RISC) will assess the participants' resilience pre and post the intervention (Burns & Anstey, 2010). For this study, we will use the 10-item questionnaire that includes questions such as: are you 'able to adapt to change,' 'can (you) deal with whatever comes,' to 'can handle unpleasant feelings.' This scale has shown good reliability and validity, with Cronbach alpha of 0.88 in 343 patients with cancer and 122 breast patients with cancer (Matzka, Mayer, Köck-Hódi, Moses-Passini, Dubey, Jahn, ... & Eicher, 2016; Scali, Gandubert, Ritchie, Soulier, Ancelin, Chaudieu, & Uddin, 2012).

Psychological Distress Symptoms:

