The Study's intervention group uses an aromatherapy inhaler, leading to a potential sensitivity to essential oils. Participants will be informed that in the case they have a sensitivity to essential oils, they need to stop using the inhaler and contact the Study PI immediately. The participant will be withdrawn from the Study and encouraged to see their healthcare provider.

There are no foreseeable participant risks or inconveniences related to participation in the research. The participants are free to withdraw at any time, and their decision to participate, refuse, or withdraw will have no impact on their treatment or any other relationship with SCCC. There is no economic burden for the participants.

The participant will be considered "lost to follow-up" if they stop communicating with the study team. The participant will also be considered "lost

to follow-up" if the participant's oncologist withdraws them from IV moderate to high emetogenic chemotherapy.

14) **Risks to Subjects***

Quality assurance will follow the University of Miami School of Nursing and Health Sciences quality assurance guidelines. These include minimizing potential harm for the participants.

The study measures include questions regarding well-being, some of which may cause emotional distress or discomfort. Participants will be informed that they may refuse to answer any question if they do not feel comfortable answering it. If a participant expresses or demonstrates emotional distress, the participant will be encouraged to contact the Sylvester Comprehensive Cancer Center (SCCC) Cancer Support Services for an appointment at [contact] or [contact].

The study's intervention group uses an aromatherapy inhaler, leading to a potential sensitivity to essential oils. Participants will be informed that in the case they have a sensitivity to essential oils, they need to immediately stop using the inhaler and contact the PI of the study, [name]. The participant will be withdrawn from the study and encouraged to see their healthcare provider.

There are no foreseeable participant risks or inconveniences related to participation in the research. The participants are free to withdraw at any time, and their decision to participate, refuse, or withdraw will have no impact on their treatment or any other relationship with SCCC. There is no economic burden for the participants.

Unanticipated Problems (Adverse Events and Serious Adverse Events) a) Definition of Unanticipated Problems

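### After first use of the inhaler, mild reactions and inhaler-linked worsening of nausea depend on volunteered report, and the event-capture rule may exclude even those reported

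*Combined protocol and SAP*

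**What the plan says.** Section 9, Antiemetic/Aromatherapy Diary, describes one rating of the inhaler's effect, completed per nausea episode: "answers include: 'it took away my nausea completely' to 'it had no effect on my nausea". The diary also has free space to name other methods used and to "describe how the CINV was controlled in the antiemetic/aromatherapy diary".

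Sensitivity is asked about twice at entry. Section 5 states that "sensitivity to essential oils will be assessed when the study team members screen and recruit a potential participant", and section 23 repeats this for recruitment. The pre-assessment checklist covers "education level), essential oils sensitivity, and risk factors of CINV"; Table 2 places it at the initial visit only.

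After entry, the Arm 2 text in section 9 says that participants "must report essential oils sensitivity to a study team" member. Section 13 says that "they need to stop using the inhaler and contact the Study PI immediately", and section 14 repeats this. A participant in whom sensitivity is identified is withdrawn. At Visits 1 and 2 the team collects the packet, goes over the instructions and deals with concerns that the participant raises. Visit 3 adds a general review of the study experience and a post-assessment questionnaire, which asks Arm 2 about the inhaler and its effects.

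On supply, the Aromatherapy Inhaler text says: "At each study visit, the study team member will offer the participant a replacement aromatherapy inhalation device". The Visit 1 and Visit 2 text provides one only where needed.

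Section 14, item c, counts inhaler sensitivity as an adverse event without a grade, and item d names a log for non-serious events. Item d(2)(b) then limits capture to inhaler-related events of Grade 3 or higher.

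**The concern.** The safeguard for the named risk is withdrawal once sensitivity is identified, so it works only as well as identification does. Sensitivity is not defined. A participant who feels more nauseated after inhaling may not see this as something to report, and the diary offers no described response for it; the nearest one is no effect. Because the inhaler is to be used whenever symptoms occur, nausea that it provoked would itself prompt further use.

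At stake is the balance of the evidence. The diary rating as described can show benefit or its absence, but not harm. If mild reactions are neither asked about nor, under item d(2)(b), captured when reported, a low count of reactions at the end of the trial would say little about tolerability.

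**Working it through.** The plan gives no figure to reproduce. The check is to take each instrument in use after first exposure and ask whether it prompts for a reaction and whether it ties worsening to the inhaler.

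| Instrument (section 9 unless stated) | When | Prompts for a reaction? | Ties worsening to the inhaler? |
|---|---|---|---|
| Diary effect rating | Each episode | No; described range ends at no effect | No |
| Diary free text | Each packet | No; worded around control of symptoms | Only if volunteered |
| MAT tool | Visits 1–3, both arms | No | No |
| Team contact, Visits 1–2 | Each visit | No; responds to what is raised | Only if volunteered |
| Study-experience review | Visit 3 | Not specifically | Possibly |
| Post-assessment | Visit 3 | General questions on the inhaler and its effects | Possibly, once |
| Self-report of sensitivity (sections 9, 13, 14) | Any time | No; volunteered | Yes |

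Table 2 has no adverse-event row, and section 12 marks safety monitoring as not applicable. The weekly contact in section 11 is between the team and the principal investigator, not with participants.

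**Timing.** Section 8 puts participation at 4 to 12 weeks, and the initial visit to Visit 3 spans three intervals. Assuming equal spacing:

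- Shortest: 4 × 7 = 28 days; 28 / 3 ≈ 9.3 days between visits.
- Longest: 12 × 7 = 84 days; 84 / 3 = 28 days between visits.

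The first direct question on the inhaler's effects other than the diary rating comes at the end of those 28 to 84 days.

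**What the MAT can show.** The protocol says: "The MAT tool consists of eight items that assess participants' CINV (i.e., occurrence, duration, and frequency"). It covers the first 24 hours and days 2 to 4, that is, 4 of roughly 9 to 28 days per interval, and it is not described as linking nausea to an inhalation. Table 2 shows no MAT at the initial visit, so there is no pre-inhaler value for the same participant. The General Approach in section 11 treats CINV as binary. A participant who would have had nausea anyway, and has more of it after inhaling, does not change on that outcome.

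**Recording.** Take a Grade 1 or 2 reaction that a participant reports. Under section 14, items c and d, it is an adverse event and goes on the non-serious log. Under item d(2)(b) it is not captured. Both cannot be followed.

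**Effect on the analyses.** Section 11 uses the MAT, the antiemetic diary data and the three psychosocial measures. The diary effect rating is in none of the listed models.

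**The case against.** The strongest reply is that several routes already exist. Participants are told to report sensitivity and stop use, and identified cases are withdrawn. Concerns about the inhaler are dealt with at Visits 1 and 2. The final questionnaire asks Arm 2 about the inhaler's effects and invites comments. The MAT would show net worsening as a difference between arms. The diary item is a relief question, not a safety endpoint, and the forms are summarised rather than reproduced, so a worsening option may be on the real diary.

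Much of this stands, and it rules out four stronger readings that a reader might infer:

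- *That no visit asks about sensitivity.* The initial visit does. The gap is the lack of a scripted question after exposure.
- *That worsening or mild reactions cannot be recorded.* Free text, the MAT, self-report and the final questionnaire can each pick up some of it. What is missing is a prompt, and attribution to the inhaler per episode.
- *That people known to react keep being supplied.* Identified sensitivity leads to withdrawal, and the visit text supplies replacements only where needed. The open question is about reactions not identified.
- *That the primary result is biased.* The rating does not enter it.

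The difference in reporting contact is also minor, since the principal investigator leads the team; it needs only a consistent instruction. What the reply does not answer is that every route before Visit 3 waits for the participant to speak first, and that item d(2)(b) may exclude what is then said.

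**Conclusion.** The point holds as a limited gap in tolerability data that should be closed; it is not a threat to the primary analysis. As described, the diary rating has no harm side, no scripted sensitivity question follows the initial visit, and section 14 contradicts itself on whether mild reactions are recorded.

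Its reach can be stated, but not the number of events missed. The allocation ratio is not given; if it is 1:1, Arm 2 has 100 / 2 = 50 participants and, with full return, 50 × 3 = 150 diaries. The documents give no rate of reaction or of spontaneous reporting, so any count of missed cases would be guesswork.

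The conclusion assumes that the summaries of the diary and post-assessment are complete. If the forms already carry a worsening option or a sensitivity item, that part falls away once the protocol says so. The conflict within section 14 remains either way.

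**What to change.** 1. In the antiemetic/aromatherapy diary, add the response *it made my nausea worse*, or state that the form already has it. Add one yes/no line with free text on any reaction to the inhaler.
2. At Visits 1 to 3, have the team member ask the existing sensitivity question and enter the answer in REDCap. Add a row for it to Table 2.
3. In section 11, state that counts of worsened episodes and of reactions will be reported beside the relief results.
4. Reconcile the passages that disagree: section 14, items c and d, with item d(2)(b) on which events are logged; the Aromatherapy Inhaler text with the Visit 1 and 2 text on replacement inhalers; and the Arm 2 text with sections 13 and 14 on whom the participant contacts. Steps 1 and 2 do not settle the recording of mild reactions unless the section 14 conflict is resolved.

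The cost is one response option, one diary line and one question at visits already held. The downside is a slightly longer diary and some nonspecific complaints to sort.
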